## **Study Protocol and Statistical Analysis Plan**

**Title: Digital Clinical Hypnosis for Chronic Pain Management**

**NCT number: NCT06050083**

**Document date: 08/21/2025**

## Study Protocol

### Overview of Study 1 and Study 2

This protocol describes two studies that are a part of this project. They use the same experimental design to evaluate the feasibility of the digital program. The primary difference is that first study (Study 1) recruits individuals with chronic low back pain and the second (Study 2) recruits individuals with general chronic pain (which includes individuals with chronic low back pain as well as individuals with chronic pain as a secondary condition to another health problem, such as spinal cord injury). Both studies aim to enroll 50 participants, which, given an estimated 20% dropout rate, would allow for complete data from at least 40 participants in each study.

Both studies use a 2-arm prospective randomized controlled trial design to evaluate the feasibility of the program (called *Rose*) over an 8-week period. Participants are randomly assigned to one of two groups: *Rose* access for a full 8 weeks (Access group) or *Rose* access for 4 weeks (Waitlist control group). The Waitlist group will not have access to *Rose* for the first 4 weeks of the study and then have access to *Rose* for the final 4 weeks. The 4-week assessment point is the primary study endpoint. Primary (feasibility) and secondary (clinical) outcomes using the *Rose* program and self-report measures using the Research Electronic Data Capture (REDCap) program, hosted by the University of Washington Institute of Translational Health Sciences (ITHS). Participants complete the self-report measures at three timepoints: baseline (before randomization), 4 weeks after randomization (primary endpoint), and 8 weeks after randomization.

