**Clinical effects analyses.** In order to estimate the possible effects of *Rose* on clinical outcomes, we will conduct two types of analyses. First, to estimate the immediate effects of the *Rose* sessions that target pain intensity, we will compute the ranges and average pre- to post-session changes in current pain intensity ratings for each participant individually (including participants in the Access condition who had access to 8 full weeks from baseline to the 8-week assessment point, and participants in the waitlist condition who had access for 4 weeks from the end of week 4 to the end of week 8 assessment point) and compute the median, minimum, and maximum of these values. Median statistics will be computed as the measure of central tendency given that the distributions of these changes were anticipated to be positively skewed (i.e., we anticipate that most participants would access *Rose* about four times during every 4-week period of access, but a fewer number might access *Rose* many times). Of interest is the general consistency of responses to the *Rose* sessions both within and between individuals. We will also conduct a linear mixed-effects model for the pre- to post-session change in pain intensity, including a random intercept for each participant to account for clustering (one for each study), to estimate the effect size and

significance levels of these changes. Given the possibility that participants who found *Rose* to be particularly effective may choose to listen to more sessions than those who found *Rose* to be less effective, as a sensitivity analysis, we will assess if there is evidence of informed cluster sizes by testing if the effectiveness of *Rose* is associated with the number of times sessions were listened to. This allows us to determine if the magnitude of the pre- to post-session improvements in pain intensity and mood are associated with frequency of listening (i.e., if those who reported more benefits tended to listen more often, which could bias the estimates of average benefit).

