Next, we will calculate the mean and standard deviation for each of the five continuous outcomes and baseline, 4-weeks, and 8-weeks stratified by treatment condition (Access vs. Waitlist group). Standardized effects will be calculated to determine the within group change between baseline and both 4- and 8-weeks as well as the between group difference in these changes. As this is feasibility study, no rigorous test of significance will be performed. However, 95% confidence intervals will be computed for the between group effect sizes to determine the range plausible effect sizes in the population.

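### Between-group clinical effects are planned only as unadjusted standardized differences in change; a baseline-adjusted raw-unit estimate, using data already collected, would usually be more precise

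*Combined protocol and SAP*

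**What the plan says.** The last paragraph of Clinical effects analyses plans means and SDs by arm and time point for "each of the five continuous outcomes". Then: "Standardized effects will be calculated to determine the within group change" from baseline to 4 and to 8 weeks, "as well as the between group difference in these changes". It plans no rigorous significance test, but does plan 95% intervals for the between-group effect sizes, "to determine the range plausible effect sizes in the population".

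No baseline covariate, between-group model, standardizing SD or interval method is named. The only model in the section is for something else: "We will also conduct a linear mixed-effects model for the pre- to post-session change in pain intensity".

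From the Overview of Study 1 and Study 2: "Participants are randomly assigned to one of two groups", with self-report measures taken at baseline, 4 weeks and 8 weeks. "The 4-week assessment point is the primary study endpoint". Enrolment of 50 with 20% dropout "would allow for complete data from at least 40 participants in each study".

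Under Measures, the secondary-outcomes paragraph says the studies are not powered for clinical outcomes. It says the estimates will help choose the domains and measures for a full trial.

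**The concern.** For the clinical outcomes, the product of this analysis is an estimate and its interval. At about 40 completers per study the interval will be wide, so precision that costs nothing is worth having. A difference in change effectively fixes the slope on baseline at 1; a model with baseline as covariate estimates it. The two have similar precision only when the true slope, r times (follow-up SD / baseline SD), is near 1.

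The unnamed SD is a second, smaller gap. The same raw effect reads differently on the baseline SD, the follow-up SD or the SD of change, so a ranking of domains by standardized effect could partly reflect the denominator. The planned arm-level means and SDs do not let a reader rebuild a raw-unit interval for the difference in change, because that needs r.

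**Working it through.** **The plan's own figure.** 50 × (1 − 0.20) = 40 completers per study, which reproduces. The plan gives no SD, correlation or interval width for the clinical outcomes, so there is nothing further to reproduce.

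**Inputs.** N = 40 completers is from the Overview. The allocation ratio is not stated; 1:1 is assumed, so n1 = n2 = 20. The correlation r (0.4 to 0.9) and the ratio k = follow-up SD / baseline SD (0.8, 1, 1.25) are assumptions. The PROMIS baseline SD is taken as 10 T-score points, the normative value given under Measures.

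**Formulas, in units of the baseline SD.**
- Planned half-width = t(N−2) × √(1 + k² − 2rk) × √(1/n1 + 1/n2)
- Adjusted half-width = t(N−3) × k√(1 − r²) × √(1/n1 + 1/n2) × √(1 + 1/(N−4)). The last factor is the cost of estimating the slope.

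**Worked case, k = 1, r = 0.4.** √(1/20 + 1/20) = 0.316.
- Planned: 2.024 × √1.2 × 0.316 = 0.701, or 7.0 PROMIS points.
- Adjusted: 2.026 × √0.84 × 0.316 × √(1 + 1/36) = 0.595, or 6.0 points.
- Ratio: 0.849, so 15% narrower.

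**Results.** Planned and adjusted half-widths, then the ratio adjusted / planned:

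| k | r = 0.4 | r = 0.7 | r = 0.8 | r = 0.9 |
|---|---|---|---|---|
| 1 | 0.701, 0.595; 0.849 | 0.496, 0.464; 0.936 | 0.405, 0.390; 0.963 | 0.286, 0.283; 0.989 |
| 0.8 | 0.640, 0.476; 0.744 | 0.462, 0.371; 0.804 | 0.384, 0.312; 0.812 | 0.286, 0.227; 0.791 |
| 1.25 | 0.800, 0.744; 0.930 | 0.577, 0.580; 1.005 | 0.480, 0.487; 1.015 | 0.358, 0.354; 0.989 |

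With 24:16 or 27:13 completers the ratios are the same; both half-widths rise by about 2% or 7%. Simulation at k = 1 (40,000 trials per setting, r = 0.4, 0.7 and 0.9) agrees with the formulas, with coverage of 0.95 for both raw-unit intervals.

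**Pain.** Entry requires average pain of at least 4, which can narrow the baseline spread. Assume a pre-entry SD of 2, a pre-entry mean of 5.0 to 6.5, the floor acting on the baseline rating itself, and a follow-up SD equal to the pre-entry SD. The adjusted interval is then 7% to 9% narrower at pre-entry r = 0.4 and 2% to 3% narrower at r = 0.7. The baseline SD falls to 1.33 to 1.47, so a 1-point effect reads 1/1.47 = 0.68 to 1/1.33 = 0.75 instead of 1/2 = 0.50.

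**Choice of SD.** A raw effect of 0.5 baseline SD, divided by the SD of change with k = 1, is 0.5/√(2(1 − r)) = 0.46 at r = 0.4 and 0.65 at r = 0.7. Divided by the follow-up SD it is 0.5/0.8 = 0.63 or 0.5/1.25 = 0.40.

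**Interval on a standardized scale.** Dividing the adjusted interval by the pooled baseline SD as if that SD were known gave simulated coverage of 0.944 and 0.943 at a true effect of 0.5 (r = 0.4 and 0.7), and 0.939 and 0.933 at 0.8. Adding d²/(2 × 38) to the variance brought it to 0.954 to 0.956. The interval should therefore allow for estimating the SD.

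**The case against.** The strongest reply is that this is a preference. The outcomes are secondary and unpowered, no decision rule depends on interval width, and the plan is silent on adjustment without ruling it out. The size of the gain rests on assumed r and SDs, and in one setting it is nil or slightly negative. All of that is true, and it is why the point is optional. It does not remove the point: the plan relies on these intervals, the change needs no new data, and the worst loss found is about 1.5%, against gains of up to 26%.

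Other objections stand and shape the fix. Naming an SD only for between-group effects would leave the within-group ones undefined. The entry floor may shrink the pain baseline SD. The pain figures assume that the floor acts on the baseline rating; it is applied at screening, and if the two ratings are separate the gain may be larger (about 12% and 5% at r = 0.4 and 0.7 with k = 1, assuming a screening-to-baseline correlation of 0.7). The addition multiplies the reported figures.

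A reader might infer that the unadjusted difference is biased. The documents do not support that: the arms are randomized, so omitting the covariate costs precision only. A reader might equally infer that the planned intervals are sound. That cannot be judged, because no SD or interval method is named, and dropout is expected with no stated missing-data method for these effects.

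**Conclusion.** The point holds as an optional, low-cost improvement. Under 20 completers per arm and r from 0.4 to 0.9, baseline adjustment narrows the raw-unit 95% interval by 15% to 1% with equal SDs and by about 19% to 26% when the follow-up SD is 0.8 times baseline. When it is 1.25 times, the result ranges from 7% narrower to about 1.5% wider. In PROMIS points with equal SDs, that is 7.0 against 6.0 at r = 0.4 and 5.0 against 4.6 at r = 0.7.

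The word 'usually' is needed, since r and the trial SDs are unknown. The feasibility conclusions are unaffected. The unnamed SD would, on its own, be a missing detail.

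**What to change.** Add to the last paragraph of Clinical effects analyses:

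- For average pain intensity, pain interference, anxiety and sleep disturbance, estimate the between-group effect within each study at 4 weeks (main) and separately at 8 weeks. Use the arm coefficient from a linear model of the follow-up score on arm and the baseline value of that measure, in raw units with a 95% interval. This estimate leads; the planned difference in change is reported alongside.
- If results by arm were already seen when this is added, the planned difference leads and the adjusted estimate is labelled as added later. The Measures section reports baseline Cronbach's alphas and a question corrected after the study began, so some data were already in hand and the timing should be stated.
- Divide all standardized effects, within and between groups, by one SD: the pooled baseline SD of that measure in that study. Use a bootstrap or delta-method interval that allows for estimating it. Note that the entry floor of 4 may shrink this SD for pain and so enlarge standardized pain effects.
- Leave opioid MME out of the linear model.
- State that at 8 weeks the Waitlist group has also had *Rose*, so that contrast is 8 against 4 weeks of access.
- Reconcile the Overview, which places baseline before randomization, with the pain-intensity paragraph under Measures, which places the baseline pain rating after it. If it is after, the pain estimates carry that caveat.

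**Cost.** No new data and one degree of freedom per model. Reporting rises to as many as four figures per outcome and time point (adjusted and planned, each raw and standardized) instead of one. Over 4 outcomes × 2 time points × 2 studies that is 64 instead of 16, so the lead estimate must be named to prevent selective emphasis.
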